OUTCOME DEFINITION: The study has two primary endpoints. The first is a process outcome and measures the activation of the hypertension care cascade – the proportion of ambulatory care consults for PLHIV at which blood pressure was screened. The second is a patient level clinical outcome – the proportion of clients eligible for hypertensive medication who attain blood pressure control. Hypertension medication eligibility was guided by a simplified risk stratification tool, but ultimately established by clinicians. This tool describes eligibility as an additive risk score of at least 3 according to the following parameters: 1) score of three for PLHIV previously on or presently initiating hypertensive medication and/or with blood pressure of at least 160/100 mmHg; score of two for blood pressure between 140/90 mmHg and 160/100 mmHg, score 1 for the presence of any number of non-modifiable risk factors (such as previous Myocardial Infarction, Coronary Vascular Disease and Diabetes Mellitus); and score of 0.33 for any number of modifiable risk factor (such as smoking, overweight, and sedentarism). Controlled hypertension is defined as blood pressure reading of ≤140/90 mmHg in clients with verified hypertension. Between these two endpoints, we also assess the proportion of patients that successfully progress from being screened, to treatment eligible, to receiving a prescription, to accessing the prescribed medication and to attaining blood pressure control.

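### Starting medication alone meets the eligibility threshold, so a first prescription places a client in both the numerator and the denominator of the eligible-to-prescription step

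*Combined protocol and SAP*

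**What the plan says.** All of the scoring is in the combined protocol and SAP, section OUTCOME DEFINITION.

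- Threshold: "This tool describes eligibility as an additive risk score of at least 3".
- Three points: "score of three for PLHIV previously on or presently initiating hypertensive medication and/or with blood pressure of at least 160/100 mmHg".
- Two points: "score of two for blood pressure between 140/90 mmHg and 160/100 mmHg".
- One point: "score 1 for the presence of any number of non-modifiable risk factors".
- A third of a point: "score of 0.33 for any number of modifiable risk factor".
- Who decides: "Hypertension medication eligibility was guided by a simplified risk stratification tool, but ultimately established by clinicians".

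The same section says that the study will assess progression "from being screened, to treatment eligible, to receiving a prescription, to accessing the prescribed medication and to attaining blood pressure control". The Descriptive analysis part of ANALYSIS APPROACH makes these person-level indicators. A client counts if ever found eligible, and if ever prescribed, within the phase of recruitment. PROCEDURES lists prescription of antihypertensive medication among the process outcomes.

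Nowhere does the plan say that eligibility is scored before the prescribing decision. Nor does it separate new initiators from clients already on treatment, or set aside clients who are eligible only because treatment was started.

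**The concern.** A step in a care cascade is meant to answer one question: of those who needed the next service, how many got it? That requires the denominator to be fixed before the service is given. Here the event being counted, a first prescription, also confers membership of the denominator.

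Consider a client at 150/95 who smokes and is not on medication. The tool gives 2 + 0.33 = 2.33, below the threshold. If a drug is started, the same client scores at least 3 and enters the step as a success. No client can enter by this route as a failure.

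At stake is the reading of a reported cascade step. SAIA-HTN shows clinics where their cascade loses patients and runs monthly improvement cycles on those losses. A clinic could appear to narrow the gap between eligibility and prescription without treating one more client who met the blood pressure and risk criteria.

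**Working it through.** **Inputs from the plan.** Threshold 3; medication (prior or starting) or blood pressure of at least 160/100, 3 points; blood pressure between 140/90 and 160/100, 2; any non-modifiable factor, 1; any modifiable factor, 0.33. The plan states no counts or proportions for this step, so there is no figure to reproduce.

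**Step 1: enumerate the scores.** Three blood pressure bands, two non-modifiable states and two modifiable states give 12 combinations.

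| Blood pressure | Scores off medication | Scores when initiating |
|---|---|---|
| Below 140/90 | 0, 0.33, 1, 1.33 | 3, 3.33, 4, 4.33 |
| 140/90 to 160/100 | 2, 2.33, 3, 3.33 | 3, 3.33, 4, 4.33 |
| At least 160/100 | 3, 3.33, 4, 4.33 | 3, 3.33, 4, 4.33 |

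Off medication, 6 of the 12 fall below 3 (0, 0.33, 1, 1.33, 2, 2.33). With initiation counted, none does. (The last column scores medication or the top blood pressure band once, as a single 3-point item. Adding the 2 blood pressure points as well would only raise it.)

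**Step 2: effect on the step.** Let E be the clients eligible without the initiation clause, P those of them prescribed, and k the below-threshold clients started on medication. The step is P/E without the clause and (P + k)/(E + k) with it. The rise is

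(P + k)/(E + k) − P/E = k(E − P) / [E(E + k)],

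which is positive whenever k > 0 and P < E, and zero when P = E.

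**Step 3: illustrate.** All counts here are assumed. With E = 100 and P = 60:

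- k = 20: 80/120 = 66.7%, a rise of 20 × 40 / (100 × 120) = 6.7 points.
- k = 40: 100/140 = 71.4%, a rise of 40 × 40 / (100 × 140) = 11.4 points.

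Prescription among those who met the criteria stays at 60%. Over a wider range, with E = 100:

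| P/E | k = 10 | k = 25 | k = 50 |
|---|---|---|---|
| 30% | 36.4% | 44.0% | 53.3% |
| 50% | 54.5% | 60.0% | 66.7% |
| 70% | 72.7% | 76.0% | 80.0% |
| 90% | 90.9% | 92.0% | 93.3% |
| 100% | 100% | 100% | 100% |

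Over the rows from 30% to 90% the rise runs from 0.9 to 23.3 points.

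**Step 4: the comparison of arms.** The observed step depends only on P/E and k/E.

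- Both the same in each arm: each arm is inflated equally and the difference is unbiased.
- Both arms at P/E = 60% with E = 100, but k = 20 against 40: the arms differ by 71.4 − 66.7 = 4.8 points (before rounding) when the true difference is zero.
- Same k = 25, starting levels of 50% and 70%: the observed values are 60% and 76%, so a true 20-point difference shows as 16.

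**Step 5: the 0.33 item.** Take clients off medication and below 160/100, with the item given once, as the text says. Without a non-modifiable factor the highest score is 2 + 0.33 = 2.33, which fails. With one, 2 + 1 = 3 already qualifies. Below 140/90 the most is 1 + 0.33 = 1.33. The item therefore changes nobody's eligibility. This rests on the once-only wording: at 0.33 per factor, three factors would give 2 + 0.99 = 2.99, but four would give 2 + 1.32 = 3.32, and the list of factors is open-ended.

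**The case against.** The strongest reply is that the score does not decide who is in the denominator. The tool guided, and the clinician decided. A reader might infer that an untreated client at 2.33 is always outside the step. The documents do not support that, since a clinician may record such a client as eligible and not prescribe. This part of the reply stands. It does not remove the overlap, because a clinician who starts treatment has in effect judged the client eligible. Prescription implies eligibility by either route. It does mean that removing the clause from the score is not enough unless the clinician-established version is reported alongside.

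Four further points stand as limits.

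- A reader might infer that the treatment effect is biased. Step 4 shows that this needs below-threshold prescribing, relative to the eligible group, or the starting level to differ by arm. The documents make that plausible but do not show it. PROCEDURES also describes guideline refreshers and job-aids as part of clinician training, which may limit such prescribing.
- A reader might infer that the affected group is large. A ceiling of 2.33 says nothing about how many clients score below 3 or how many of them are treated.
- A reader might carry the argument to the second primary endpoint, which also uses eligible clients. Control is defined only among clients with verified hypertension, a term that the plan does not define, so whether these clients count there cannot be settled from the text.
- The text does not say whether initiation means prescription or pick-up. If it means pick-up, then on the tool alone the overlap moves one step down the cascade.

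Finally, the full cascade description is in the descriptive part of the analysis, and the process outcome for prescription is not given an explicit denominator. That limits the seriousness but not the logic.

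**Conclusion.** The point holds as a defect in the definition of one reported cascade step. As written, anyone started on medication is eligible by construction, so the eligible-to-prescription proportion has a denominator that depends on its numerator. The direction is certain when the step is below 100% and any below-threshold client is started on medication: the proportion is raised. The size cannot be known from the documents, and every count above is an illustration. Distortion between arms is possible and plausible, not demonstrated.

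The 0.33 item is a secondary matter. An item that cannot alter the classification under its own wording contradicts no other passage, but it is reason to check that the score in the plan is the score the clinics used.

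Nothing here concerns who should be treated. It concerns only how clients are classified for analysis.

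**What to change.** 1. For the eligible-to-prescription step, classify eligibility from blood pressure, risk-factor items and medication use recorded before the client's first in-study prescribing decision. Give no points for initiation.
2. Do not let a prescription first issued in the study count later as prior use. Otherwise, under the ever-eligible and ever-prescribed rule, a below-threshold client prescribed at one visit is previously medicated at the next and returns to both numerator and denominator.
3. Report this version beside the clinician-established one, and count separately by arm the clients who are eligible only through initiation or clinician judgement.
4. State whether initiation refers to prescription or to pick-up.
5. Reconcile the score text, including the 0.33 item and the threshold, with the tool used at sites before any score is computed.

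The cost is some SAP wording, one derived variable and one extra table row. There are two downsides. Some clients whom clinicians judged eligible move to the separate count. The derivation also assumes that the tool's items, and prior use as distinct from initiation, were recorded individually. The plan says that patient-level hypertension data were collected at every ambulatory visit but does not confirm that detail. Data collection is described as complete, so the new version should be labelled as specified afterwards. If the items cannot be separated, the plan should say so and describe the step as conditional on a denominator that includes everyone treated.

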SAIA-HTN STUDY PROTOCOL AND STATISTICAL ANALYSIS PLAN

TITLE: Systems Analysis and Improvement Approach to Optimize the Hypertension Diagnosis and Care Cascade for HIV-infected Individuals (SAIA-HTN)

NCT: STUDY00006694

Date of Document: 10/23/24

STUDY OBJECTIVE: The overall goal of this application is to evaluate a model for systematic assessment and improvement of HTN diagnosis and management services for people living with HIV (PLHIV) in Mozambique.

STUDY DESIGN: Over the five-year project, we will conduct a parallel cluster randomized trial to evaluate the effectiveness of SAIA-HTN. We will use qualitative methods (focus group discussions and in-depth interviews with health workers) to identify drivers of SAIA-HTN's implementation success and collect data to determine the intervention's costs and cost effectiveness on HTN and HIV performance measures.

BACKGROUND: Undiagnosed and untreated hypertension (HTN) is one of the largest drivers of cardiovascular disease (CVD), which contributes to one third of deaths globally (and disproportionately affects low and middle income countries (LMICs)). A systematic review across sub-Saharan Africa (sSA) reported HTN prevalence between 14.7-69.9% (median prevalence 29%). In Mozambique (a low-income country with >13% adult HIV prevalence), HTN prevalence among adults increased sharply from 2005 to 2015, now affecting nearly 40% of adults. Yet just 14.5% are aware of their HTN status (the lowest in sSA); among these, only 50.1% are in treatment, less than half of whom have controlled HTN. As a result of this leaky cascade, only 3% of the adult population with HTN in Mozambique have their condition controlled.

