We described health facility characteristics at baseline and the study participant population both during baseline, and at the time of recruitment for each study phase, in terms of sex, age and hypertension care outcomes status. For the primary process outcome, we describe the number and proportion of outpatient consultations at which blood pressure was screened in each study phase. To describe the hypertension care cascade, we ascertain the proportion of patients who, within the phase they are recruited, are ever screened and diagnosed as eligible for hypertensive treatment, ever receive a prescription and pick-up the medication prescribed, and who present controlled blood pressure control in the last two ambulatory consultations (if same outcome observed in both visits) or in most consultations. Ambulatory consultations beyond the phase of recruitment are censored.

Inferential analysis

To assess the effect of SAIA-HTN, we ascertained clinical outcomes in all ambulatory care visits within each phase (observations attributed to the phase in which consultations took place), and estimated the population level risk of the outcomes using Generalized Estimation Equations (GEE) and Log-binomial or Poisson regressions, assuming an exchangeable correlation structure to account for clustering at the level of health clinic, and adjusted for study phase and for whether patients were newly recruited or retained from a prior study phase (Model 1).

Model 1: $log(E[yij]) = \beta_0 + \beta_1 \cdot x_{ij} + \beta_2 \cdot phase_{ij} + \beta_2 \cdot recruitment_{ij} + u_{ij}$

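### The reading that makes a client eligible is not excluded from the control outcome, so the arm that measures blood pressure more often can show better control with no treatment effect

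*Combined protocol and SAP*

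**What the plan says.** The OUTCOME DEFINITION section gives the second primary endpoint as "the proportion of clients eligible for hypertensive medication who attain blood pressure control" and calls it a patient-level clinical outcome. It adds: "Controlled hypertension is defined as blood pressure reading of ≤140/90 mmHg in clients with verified hypertension".

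A client is eligible at a score of at least 3. One route is "score of three for PLHIV previously on or presently initiating hypertensive medication and/or with blood pressure of at least 160/100 mmHg". Another combines two entries: "score of two for blood pressure between 140/90 mmHg and 160/100 mmHg, score 1 for the presence of any number of non-modifiable risk factors". The tool guides eligibility, which is "but ultimately established by clinicians".

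Under ANALYSIS APPROACH, Inferential analysis, the effect is estimated from visits: "we ascertained clinical outcomes in all ambulatory care visits within each phase". Model 1 adjusts for study phase and for new or retained status, with clustering by clinic. It has no term for the eligibility visit or for the number of readings. The Descriptive analysis has a client-level rule, which takes control from the "last two ambulatory consultations (if same outcome observed in both visits) or in most consultations". Neither part sets a start point after eligibility.

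**The concern.** A client who is not on medication and qualifies on blood pressure does so with a high reading. That reading precedes any treatment and is above the control threshold, apart from the 140/90 boundary. If it is scored as an outcome, each such client brings one near-certain failure. A client read once contributes only that failure. A client read four times contributes the same failure and three further readings, which can be controlled through treatment or through regression to the mean after selection on a high value.

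The number of readings per client is what the intervention is meant to change, since screening per consult is the first primary endpoint. Success on the first endpoint could therefore produce apparent success on the second, which carries the trial's clinical claim. The problem would remain if visits without a reading were dropped and both arms held the same clients.

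**Working it through.** **The plan's own figure.** The plan gives no figure for control. Its sample size section gives a detectable difference in screening of 15 to 29 points, which I use only for plausible screening rates. A two-proportion formula with design effect 1 + (m − 1) × ICC, pooled variance, 1000 visits in total (62.5 per clinic) and t on 12 df gives 14.7 to 28.9 points. With 1000 visits per clinic it gives 11.5 to 25.2 (normal) or 12.5 to 27.3 (t, 14 df). The match was found by trying variants, so the plan's method is not confirmed.

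**Inputs for the bias**
- Control-arm screening 10 to 20% of consults, and a difference of 15 to 29 points (SAMPLE SIZE AND RANDOMIZATION). Base case: 15% against 40%.
- Share already treated, s: BACKGROUND says of adults with hypertension that "just 14.5% are aware of their HTN status", and 50.1% of those are treated. 0.145 × 0.501 = 0.073.
- Assumed, not in the documents: k = 8 visits per client in the phase; 50% true control at any later reading in both arms; the same screening probability p at every visit; the first reading of an untreated client is the qualifying one.

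**Formulas**
- Mean readings among clients with at least one: kp / [1 − (1 − p)^k].
- Qualifying share of readings, Q: the inverse of that mean.
- Observed control: 0.5 × [1 − (1 − w)(1 − s)Q], where w is the share of readings from clients who became eligible in an earlier phase.

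**Base case (w = 0)**
- Control arm: 1.2 / (1 − 0.85^8) = 1.65 readings, Q = 0.606; observed control 0.5 × (1 − 0.927 × 0.606) = 21.9%.
- Intervention arm: 3.2 / (1 − 0.60^8) = 3.25 readings, Q = 0.307; observed control 35.8%.
- Risk ratio 1.63, with identical true control.
- Clients with only the one reading, kp(1 − p)^(k − 1) / [1 − (1 − p)^k]: 53% against 9%.

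**Sensitivity**

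| Change from base case | Observed control | Risk ratio |
|---|---|---|
| 40% already treated | 31.8% vs 40.8% | 1.28 |
| w = 0.5 | 35.9% vs 42.9% | 1.19 |
| w = 0.75 | 43.0% vs 46.4% | 1.08 |
| Screening 50% vs 70% | 38.5% vs 41.7% | 1.085 |
| Screening 70% vs 85% | 41.7% vs 43.2% | 1.035 |

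With w = 0, 4 to 12 visits, screening pairs 10/25, 15/40, 20/35 and 20/49%, and 7% or 40% already treated, the ratio runs from 1.12 to 1.90.

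**Simulation with no treatment effect.** This used 16 clinics, 400 clients each, 8 visits, readings counted from eligibility on, Poisson GEE with exchangeable correlation by clinic and an arm term only, and 150 runs per row. Assumed systolic mean 125, between-person SD 17, within-person SD 12, and 30% with a non-modifiable risk factor. 'Treated' is the share of hypertensive clients already on medication.

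| Screening | Treated | Ratio, rejection: eligibility reading kept | Ratio, rejection: reading dropped |
|---|---|---|---|
| 20% vs 20% | 7.3% | 0.99, 11% | 0.99, 9% |
| 20% vs 49% | 7.3% | 1.57, 100% | 1.09, 16% |
| 20% vs 49% | 30% | 1.37, 95% | 1.08, 21% |
| 50% vs 90% | 7.3% | 1.24, 91% | 1.07, 27% |
| 70% vs 80% | 7.3% | 1.05, 24% | 1.02, 12% |

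The equal-screening row shows that few clusters explain only a small part of the false rejections. Dropping the reading leaves a small residual, because more readings also bring in milder clients who cross the threshold later.

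**Client-level rule.** With later readings controlled 40% of the time, the eligibility reading 3%, and ties scored as not controlled, the rule gives 3.0% for one reading. For two readings it gives 0.03 × 0.40 = 1.2%. Three give 17.4% and four give 16.6%.

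**The case against.** A reader might infer that the plan states that the eligibility reading counts as an outcome. It does not. That follows from the all-visits wording and the absence of an exclusion. Speaking of clients who attain control, and of verified hypertension, could mean later readings only. This stands, but two analysts could then obtain different primary results, so the text needs settling either way.

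A reader might also infer that every eligibility reading is a failure. Clients previously on medication and clinicians' own decisions are exceptions, and the 7% treated figure is for the general adult population, not for eligible PLHIV. This stands as a limit on size.

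The strongest objection is that the 1.63 rests on favourable inputs. The intensive phase lasts 24 months and the sustainment phase 12, and the model includes retained clients, whose eligibility reading may lie in an earlier phase. Every consultation room received a sphygmomanometer, clinicians had refresher training, and data collection carried an incentive, so control-arm screening may exceed the planning range. Clients already flagged as hypertensive may also be measured more often in both arms. All of this can shrink the bias. None of it reverses the direction while the intervention arm has more readings per client.

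Finally, counting a client who was never re-measured as not having attained control is a legitimate choice for a care cascade, and with three or more readings a concordant last pair already bypasses the eligibility reading. That answers much of the worry about the client-level rule, which is descriptive. It does not answer the worry about the visit-level effect model.

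**Conclusion.** The concern holds for the visit-level analysis of the second primary endpoint. As written, the plan lets the eligibility reading count. Where the intervention raises readings per client, the endpoint is biased in its favour with no treatment effect.

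The size cannot be fixed from the documents. A 1.6-fold spurious gain should not be read as the expected bias: 1.63 requires 8 visits per client, screening at 15% against 40%, 7% already treated, and all untreated clients becoming eligible within the phase. With half or three quarters of readings from clients eligible earlier it is 1.19 or 1.08, and with high screening in both arms about 1.035 to 1.085. Small ratios can still matter: at 70% against 80% screening, the simulation rejected a true null in 24% of runs, against 11% with equal screening at 20%.

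**What to change.** In OUTCOME DEFINITION and ANALYSIS APPROACH, state that the reading at the visit where eligibility is first recorded is the client's baseline and is not scored as a control outcome, and that control is scored only from later visits. Apply the same start point to the descriptive client-level rule. Report by arm the number of readings per eligible client and the share with no later reading.

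Scoring only re-measured clients loses clients unequally by arm (53% against 9% in the base case). So add a client-level analysis with all eligible clients in the denominator, where no later reading means control not shown. That analysis still rewards re-measurement, so it describes demonstrated control in the cascade and should be read beside the later-visits analysis. Keep the all-visits analysis as a sensitivity analysis. Do not impose a fixed window such as 6 months after eligibility, because the 3-month baseline period cannot accommodate it.

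The cost is a wording change and one derived variable from visit data already collected. There will be fewer readings, and a small residual bias from unequal numbers of readings remains (simulated ratios of 1.02 to 1.09). The document is dated 10/23/24 and describes the trial as already conducted, so the change should be labelled with its date.
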